#### 2.4 Ethical considerations

Similar ethical considerations will apply to this trial as applied in our feasibility study with psilocybin, with the additional consideration that half of the patients will receive two psychedelic doses of psilocybin (i.e. 25mg), 3 weeks apart, the first one followed by daily placebo for 6 weeks, and half will receive two inactive doses of psilocybin (1mg), 3 weeks apart, the first one followed by 6 weeks of daily escitalopram (10mg for three weeks and 20mg for three weeks). Knowledge gained from our feasibility study [1], discussions with researchers leading other randomized control trials in this area [5] and previous clinical trial literature on escitalopram [98] has directed the design of this trial.

The main study risks include: standard risks associated with an acute high dose of psilocybin (e.g. potential acute anxiety and the need for psychological support and supervision during the experience), standard side-effects associated with escitalopram (e.g. drowsiness, dizziness, sleep problems and potential for withdrawal symptoms upon cessation), and standard concerns regarding placebo treatment in depression [7]. Establishing a good connection with referring clinicians, and following standard procedures for psilocybin research [70], will help to manage and mitigate its particular risks.

#### 2.4.1 Managing risks related to withdrawal from antidepressants

PSILODEP RCT – Study Protocol, Version 7, 11/07/2019

Serotonergic antidepressants are known to attenuate the acute psychological effects of psychedelics [8] and thus, we feel it is necessary that patients withdraw from these medications in order to experience the full effects of the 25mg dose of psilocybin. This washout component of the design is consistent with our recent pilot study, as this was done safely and effectively in that trial. Withdrawal symptoms and a worsening of depressive symptoms can occur with antidepressant-withdrawal [9]; thus, we will incorporate a number of contingency measures to reduce associated risks, namely:

1) Patients will be free to leave the study at any point and return to their treatment as usual if they, their mental-health care-giver or the study team feel this is the right course of action.

2) The study blind will be broken at 6-weeks after the initial dosing session (fig 1), enabling patients to return to pre-study treatment/s if they so choose.

3) Study clinicians will offer telephone contact to patients during the withdrawal period, if this is required.

It is important to note that since recruitment to this trial is not restricted to patients with treatment-resistant depression, potential volunteers may well be unmedicated at the time of study entry. Thus, we can anticipate that challenges relating to withdrawal from medication will be less than in our previous open-label trial in treatment-resistant depression. Even so, antidepressant medication withdrawal was managed safely and effectively in that trial and we foresee that the same will be true in this trial.

## 2.4.2 Managing risks related to psychedelic treatment

Before, during and after the dosing sessions, patients will receive psychological support from clinicians with experience of providing psilocybin treatment in the context of research studies, including clinical trials. On the dosing day, patients will only be allowed to return home once the study psychiatrist is confident they are fit to do so, and signs the patient out. Taxis will be ordered to take patients home. Patients will be asked to text or call us when they return home.

We will ask that the patient have a friend or family member at home, when they return. We will ask for this 'chaperone's' contact details so that we can contact them if we cannot manage to contact the patient themselves.

Both the patient and their chaperone will be encouraged to contact us should any problems arise. In this way, any concerns in the immediate period or thereafter can be easily brought to our attention. Twenty-four-hour emergency contact numbers will be provided.

Overnight accommodation facilities are available onsite at Imperial, which are booked in advance. Patients who do not have a chaperone at home will be encouraged to take advantage of the onsite accommodation. Similarly, patients who travel to us from outside of London will be encouraged to take advantage of the onsite accommodation and a friend or family member can also be accommodated.

#### 2.5 Procedures

The patient's immediate care team will be made aware of the study and will identify a patient and ask them if they are willing to be contacted by us. The primary caregiver will then inform us of any patients who are interested in participating and provide a contact telephone number and/or email. The patient will be issued with an A4 summary sheet containing a brief summary of the study and our contact details. The more comprehensive information sheet will also be made available to them. After the patient has initiated contact with us, we will inform them of the nature of the study and organise an appropriate time for an initial telephone screen. We will ask the patient if we can contact their GP/psychiatrist and this will be done via an email using a standard letter template.

Eligibility will be principally determined by the study psychiatrist who will thoroughly screen all patients to identify and confirm the presence of major depression and exclude other conditions. Supporting information from relevant mental health professionals and/or general practitioners will be sought prior to entry into the trial to confirm diagnosis and ensure that all patients meet the inclusion criteria.

If the patient appears to be eligible (post-telephone screen and post-contact with their GP/psychiatrist), a date for the first screening visit will be arranged. This will be a meeting with the study psychiatrist to review patient history, current symptoms, and to further check inclusion and exclusion criteria.

There will be around 4 weeks from first screening visit to the first study day visit to allow analysis of screening data (e.g. blood tests) to determine eligibility and enable contact to be made between their GP and/or mental health practitioners, and so that proper and cautious washout of antidepressant (4 weeks for fluoxetine and 2 weeks for other antidepressants) can be done, where applicable. If no medication washout is required, the time from screening to study day one can be shorter than 4 weeks, although we will strive to acquire weekly QIDS ratings as soon as the patient's entry into the trial is confirmed. In cases where medication washout is required, if symptoms show a marked increase in relation to the cessation/tapering

of medications, we will discuss with the patient and their GP or mental health caregiver whether the patient should withdraw from the trial so that previous medications can be resumed or new ones given. There will be ~7 weeks from the first (post-screening) study visit (**visit 2, scan 1**) to the primary end point/blind broken (**visit 7**), after which patients may return to their normal treatments if they so wish.

Patients will be required to make **7 visits** (see fig. 2). Patients will be assessed for up to six months after the initial dosing session; however, the study blind will be broken 6 weeks after the dosing session. Treatment as normal can then take place after the study blind has been broken.

## 2.6. Visits

## Visit 1: Screening

Screenings typically take up to **4.5 hours** and include a physical examination by the study doctor, an ECG, and a period of MRI scanner acclimatisation, i.e. the patient will be invited to spend a period lying in an MRI scanner to assess whether they can tolerate the environment/conditions. Consent to enter the study will be sought from each participant after a full explanation has been given, the study information sheet has been issued and time allowed for consideration. Signed informed consent will be obtained for each patient.

We will know whether or not the patient is eligible for the trial ~3-days post screening (depending on receipt of relevant confirmation of diagnosis from the patient's GP or psychiatrist). As soon as eligibility is confirmed, the patient will be randomly allocated to one of the two study conditions.

If eligible, and if the patient wishes to participate in the trial, as soon as study entry is confirmed, a patient taking antidepressant medication will be required to begin coming off this medication, in a gradual, tapered fashion. We will ask that they inform their primary care giver of their decision to do this and we will manage medication withdrawal with their awareness. Medication withdrawal is typically done via gradual titration (e.g. halving of dose in first week) and the study psychiatrist will oversee this process in correspondence with the patient's GP and/or psychiatrist.

As soon as entry into the trial is confirmed, patients will be asked to complete the weekly QIDS-16 [12].. Patients will complete this up until the 6-week post dosing day, when the blind is broken. Use of the QIDS-16 [12] will enable us to track patient's mental health for the duration of the trial, facilitating patient monitoring and safety, while providing potentially useful data on weekly mood cycling pre versus post treatment [42].

## Blood will be collected at baseline for the following routine blood tests:

- Full Blood Count (haemoglobin, total white cell count, lymphocytes, neutrophils, platelets)
- Renal panel (creatinine, urea, estimated GFR)
- Biochemistry (Sodium, potassium, adjusted calcium, phosphate, albumin and total protein)
- Liver panel (total bilirubin, alanine transaminase, GGT)
- Amylase

We will exclude participants on the basis of a clinical significant abnormality in any of the above tests at screening. In particular, we will aim to exclude participants with any form of renal or hepatic impairment, in accordance with the cautions raised in the escitalopram SmPC [100], see section 7.2.1.

As well as collecting blood for the above, we will also ask participants if we can acquire a sample for subsequent genetic analysis (not required for enrolment, only encouraged). Whole blood for genetic analysis will be collected in 2 x 8.5ml 'PAXgene' tubes and frozen at -20C. At the end of the study, samples will be transferred to the labs of the MRC Social, Genetic & Developmental Psychiatry (SGDP) Centre at The Institute of Psychiatry, Psychology and Neuroscience (IoPPN) in Denmark Hill, South London, with whom we have a material transfer agreement. [name] and [name] will act as custodians for the samples and both tissue bank and HTA licenses are already in place. The samples will be stored in locked -80C freezers in the SGDP labs, to which access is only given to authorised personnel and with full audit capabilities.

The purpose for collecting whole blood is to enable genetic analysis in the longer term. Candidate gene and genome wide association analyses require high numbers of samples to achieve adequate statistical power in analysis. Therefore, these samples form the first batch of a larger sample acquisition effort in this area. Our main aim is to perform association testing between functional polymorphisms of the 5-HT2A receptor, hypothesising that these may be associated with response to treatment. For example, the T102C polymorphism of the 5-HT2A receptor has been associated both with suicidality in depression [92] and schizophrenia [93] raising the interesting question of whether the 2 alleles at this locus may have a bidirectional association with response to psychedelics.

Whole blood samples for genetic analysis will be stored for up to 5 years in the first instance, however this will be subject to renewal depending on the progress of the wider project. Participants may request that their samples be destroyed at any time by notifying the PI of the

study in writing. Samples would then be destroyed by incineration. Participants will not receive results of genetic testing, as candidate gene analysis is vanishingly unlikely to have any clinically significant outcome for individuals.

#### Visit 2: Scan 1/Prep

The scanning procedure takes approximately 2.5 hours, with the scan itself lasting for no longer than 90 minutes. The scan session will be followed by psychological preparation with the therapy team (two individuals) who will sit with the patient during their dosing session. Psychological preparation will take approximately 3 hours, with two breaks. This visit will take approximately **5.5 hours** in total.

#### Visit 3: Dosing session 1

The dosing session will take place the day after scan 1. Depending on the results of randomisation, the patient will receive either 25mg (conditions 1) or 1mg psilocybin (condition 2) in the morning. After their dosing session is over, they will be given either placebo capsules (condition 1) or 10mg escitalopram capsules (condition 2) to take home with them. The dosing day will typically run for ~8 hours and involve: arrival at 9am, initial preparation, including relaxation techniques. Dosing at 10:30am. Drug effects (25mg only) are typically experienced for 5-6 hours (i.e. subsiding to a low-negligible level at 3:30-4:30pm). Depending on the magnitude of residual drug effects, patients will be asked to complete questionnaires from 3:30pm onwards and take part in a filmed and audio recorded structured interview at ~4:30/5pm (consent for this is included in the consent sheet – and with consent, all visits will be filmed as default). A study psychiatrist will assess the patient for potential discharge. If the patient is to travel home, a taxi will be ordered. Patients will typically leave the study centre around 5:30/6:00pm.

[figure not shown]

Fig 2. Dosing day timeline

At the end of the first dosing session, patients will be given a course of capsules to be taken daily (upon waking) for the following 6 weeks. Randomisation will determine whether these capsules are to be escitalopram or placebo. Patients will be asked to take their first capsule as close to **8:00am** as possible the morning after the first dosing session and document exactly when it was taken, to ensure standardisation of peak plasma concentration where relevant (i.e. escitalopram condition). N.B. peak plasma concentrations of escitalopram are reached 3-4 hours post-ingestion [10]. Each patient will take one capsule each day for the first 3 weeks and two for the remaining 3 weeks, regardless of whether they are in condition 1 or 2.

#### Visit 4 (time since first dosing session = 1 day)

**One day** after dosing, patients will be asked to complete some questionnaires (including a daily version of the QIDS [82]) and will also take part in a structured interview/integration session. Patients will be asked about their experiences the previous day, how they slept, how they have felt today etc. This visit will take approximately 2-3 hours in total.

Interim period (1 week post-treatment): phone call or Skype/Zoom session to check in with patient. Remote assessments of the QIDS also done weekly throughout the trial. Assessments will be cued via email and/or text (using the Psychedelic Survey platform) and completed electronically (on Survey Gizmo), where the study team can access them.

#### Visit 5 (time since first dosing session = 3 weeks): Dosing session 2

The second dosing session will take place exactly as described in Visit 3/Fig 2 above.

Interim period (4, 5 and 6 weeks post-dosing session 1): remote assessments will continue as before, cued via email and/or text (using the Psychedelic Survey platform) and completed electronically (on Survey Gizmo), where the study team can access them. Patients are free to communicate via email with the study team at any point if issues arise. If additional support is needed, each patient will be allowed a maximum of two additional Skype/Zoom sessions with the study team. This limit is in place in order to avoid an imbalance in the amount of support patients receive.

#### Visit 6 (1 day post-dosing session 2):

This visit will follow the same structure as visit 4 (1 day post-dosing session 1), described above.

# Visit 7 (time since first dosing session = 6 weeks/time since second dosing session = 3 weeks)

The final study visit will take place 6 weeks after the first dosing session. This visit will include a final MRI scan. Patients will arrive at 10am and be scanned at 11am. The scanning session will last for no longer than 90 minutes. After this, patients will be asked to complete some questionnaires and will take part in a structured interview in which they will be asked how they have felt today and the past 6 weeks. The HAM-D and MADRS assessments will be performed which enquire about depressive symptoms over the last week. A comprehensive side-effects questionnaire will also be completed, which asks about side-effects over a 6-week period [11]. A second ECG scan will also be conducted in order to ensure no effect of either drug on heart physiology and a repeat routine blood test will be done (see above for a complete list of tests). This visit will take approximately 5 hours in total. At the end of this visit, we will inform the patient of the condition they **were** enrolled in; thereby breaking the blind. Breaking the blind at this time point will enable us to assess treatment safety and efficacy for both conditions

and provide the patient with information on what they have received - which may then inform future decisions regarding treatment, e.g. whether or not they want to continue with escitalopram if they were in condition 2.

Study Timeline			
Date	Event	Main assessment/s	Approximate Duration
Visit 1	Screening	QIDS, HAM-D MADRS, ECG	5 hours
Visit 2	Scan 1	QIDS, HAM-D, MADRS, scan measures	5 hours
Visit 3	Dosing session 1 (DS1)	ASC, EDI, etc	8 hours
Visit 4	1-day post DS1	QIDS, interview	2-3 hours
Visit 5	Dosing session 2 (DS2)	ASC, EDI, etc	8 hours
Visit 6	1 day post DS2	QIDS, interview	2-3 hours
Visit 7	Final visit + scan 2 6-weeks post DS1	QIDS, HAM-D, MADRS interview, ECG, scan measures	5 hours

At the end of Visit 7: patients will be told by the study team that a documentary is being made about the study that they could participate in if they chose to. If they are interested in finding out more information, they will be taken to meet the Imperial Press Office team in person. The Imperial Press Office team will talk to them about the nature of the documentary and the implications of participating. Participants will be given an information sheet/consent form to read and sign if they are interested, as well as an information sheet about the film producers Grain Media. If participants are keen to be involved or would like to find out more, they can also meet the Grain Media team in person, who can tell them more about the documentary process. If participants agree to sign the consent form, this will prompt the study team to release the footage that has been filmed in the trial to Grain Media. If participants choose to not sign, the footage remains only for use within the Imperial team (the data 'controllers'), for training purposes, as agreed in the initial consent form signed at the start of the study (unless further consent to share is sought from patients).

Assessments at 1-6 months Visit 7: remote assessments of the QIDS-16 will be done monthly at 1-6 months post-treatment. More comprehensive assessments will also be done

1, 3 and 6 months after the initial dosing session. Assessments will be cued by telephone and email and completed electronically and emailed back to the study team. A member of the study team will speak with the patient via telephone or skype at these time points.

**1 month post Visit 7:** A structured interview will be carried out via Skype, telephone or in person if the patient prefers this. This will focus on the patient's overall experience of the trial, looking back on it as a relatively recent experience, and on how they are doing 1 month later.

6-months post Visit 7: Remote assessments will be done (as at 3 months) and a structured interview will be carried out and recorded, either via skype, telephone or in person, if the patient prefers. This will focus on the patient's perception of the value of the trial with the benefit of 6 months of hindsight and on how they are doing now. See Appendix 1 for semi-structured interview protocol.

If, at any point after the final formal study visit, we become concerned about a patient's mental state and associated risks, we will liaise with their GP and/or mental health practitioners - who may then decide to implement appropriate interventions, if this is indicated.

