#### 1. Aim of study

The aim of this study is to compare the mechanisms, tolerability and efficacy of two high doses of psilocybin versus a 6 week course of a leading antidepressant medication, escitalopram, in major depressive disorder (MDD). This will be a 2-arm, active comparator, double-blind randomised control trial in a total of 60 completing volunteers ('completing' measured by primary outcome measure).

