## 1.1. Basic study design

The main experimental condition (**condition 1**) in this study will involve two high doses of 25mg psilocybin (per os, p.o.), 3 weeks apart. The first dose will be followed by 6 weeks of daily (inert) placebo capsule ingestion (condition 1, fig. 1). The control condition (**condition 2**) will involve two dosing sessions, also 3 weeks apart, with a presumed inactive dose of

psilocybin (1mg p.o.). The first dose will be followed by 6-weeks of daily escitalopram capsule ingestion (fig. 1).

Thus, there will be a dedicated on-site dosing day for both conditions (named here 'initial dosing session') followed by 6 weeks of daily capsule ingestion at home and a second dosing session 3 weeks after the first. The primary endpoint for assessing efficacy is 6 weeks after the initial dosing session, when the blind will be broken at the final study visit. Unblinded follow-up will occur for a further 6 months to assess safety and any potential enduring effects.

The main purpose of this design is to test the hypothesis that two doses of psilocybin, a design similar to what may be done in future therapy, will show a superior efficacy to escitalopram and crucially, a different *mechanism of action*. Secondarily, we predict that conditions 1 and 2 will show comparable efficacy at 6 weeks but with a different side-effect profile, e.g. we predict that changes in sexual dysfunction will be different across conditions and that psilocybin will act more rapidly to alleviate depressive symptoms.

Regarding the primary outcome, we will use functional magnetic resonance imaging (fMRI) at baseline and six weeks after the initial dosing session to identify how brain activity changes before and after two doses of 25mg psilocybin vs 6 weeks of daily escitalopram.

We predict that fMRI measured amygdala blood oxygen level dependent (BOLD) responses to emotional faces after-versus-before treatment will be greater in condition 1 (psilocybin) than in condition 2 (escitalopram).

This trial promises to significantly advance our knowledge of the safety, efficacy and mechanism of action of psilocybin for MDD by comparing it with a major conventional treatment for depression. The comparison with escitalopram adds an important component to this trial which may ultimately lead to the development of psilocybin as an alternative treatment option for patients with MDD.

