#### 2.7. Psychological outcome measures

Measures completed before and after treatment will include the following:

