## Common (i.e. ~10% at 20mg):

- 1) Agitation or restlessness
- 2) Diarrhea
- 3) Difficulty sleeping
- 4) Drowsiness
- 5) Dry mouth
- 6) Headache
- 7) Nausea
- 8) Sexual difficulties (decreased sexual ability or desire, ejaculatory delay)
- 9) Dizziness
- 10) Sweating

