## Less common (< 10%)

- 1) Frequent urination
- 2) Indigestion
- 3) Increased or decreased appetite
- 4) Taste alterations
- 5) Tremor (shaking)
- 6) Tingling in arms or legs
- 7) Weight changes
- 8) Influenza-like symptoms and pain in neck or shoulders
- 9) Serotonin syndrome
- 10) Suicidal thinking and behavior
- 11) Abnormal bleeding
- 12) Seizures
- 13) Manic episodes
- 14) Low sodium
- 15) Angle closure glaucoma

The MHRA recommends that escitalopram should not be used in patients with known QT interval prolongation (above 440ms in men and above 470ms in women) or in combination with other medicines known to prolong the QT interval. An ECG during the screening visit will ensure that such individuals will be excluded from the study. To prevent antidepressant discontinuation syndrome, gradual withdrawal from escitalopram will be managed by the study psychiatrist in consultation with the patient's GP/psychiatrist.

In the event of signs of cardiac arrhythmia (fluttering in chest, tachycardia, bradycardia, chest pain, shortness of breath, lightheadedness, etc), patients will be advised to contact us and their GP immediately and stop escitalopram dosing. In this case, we would schedule an extra visit and perform an extra ECG.

Additionally, the Summary of Product Characteristics (SmPC) for escitalopram [100] advises caution in patients with severely reduced renal function (CLCR less than 30 ml/min). We are aiming to recruit depressed patients who are otherwise physically healthy and will be excluding patients with severely reduced renal function as per exclusion criteria.

The SmPC for escitalopram [100] also raises cautions about its use in patients with hepatic impairment. In the case of mild or moderate hepatic impairment, dose reduction is necessary. For consistency, patients with any form of hepatic impairment will be excluded (see section 4.2.4). Liver Function Tests (LFTs) conducted in screening will provide the study medical doctor with the necessary information to make this assessment.

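### The comprehensive side-effects questionnaire has no stated pre-dose administration, so on this instrument symptoms present at entry can be counted as side-effects

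*Protocol*

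**What the plan says.** Section 1 gives the purpose of the trial as to "compare the mechanisms, tolerability and efficacy of two high doses of psilocybin" with those of escitalopram. Section 1.1 foresees two efficacy outcomes. The main hypothesis is that psilocybin "will show a superior efficacy to escitalopram"; the secondary prediction is that "conditions 1 and 2 will show comparable efficacy at 6 weeks but with a different side-effect profile".

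The broad side-effects instrument appears in section 2.6 under Visit 7: "A comprehensive side-effects questionnaire will also be completed, which asks about side-effects over a 6-week period". It is not mentioned in the text for Visits 1 to 6, in the Study Timeline, in the screening list of section 4.2.3, or in the section 2.7 list introduced by "Measures completed before and after treatment will include the following".

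Section 7.2.1 lists expected escitalopram effects. The common ones include "Difficulty sleeping", agitation, drowsiness and reduced sexual desire. The less common ones include "Increased or decreased appetite", weight change and suicidal thinking.

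**The concern.** Patients enter with moderate to severe depression (HAM-D of 17 or more), and some enter after antidepressant washout, which section 2.4.1 says can bring withdrawal symptoms. Many will therefore already have sleep, appetite or agitation problems before the first dose. A questionnaire given at week 6 and looking back over the whole treatment period, with no earlier score, has no record that separates these from symptoms that began on treatment.

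Two consequences follow. Pre-existing symptoms add the same background to both arms and make a true difference in new symptoms harder to see. And if one arm has less residual depression at week 6, it may report fewer such symptoms and look better tolerated although neither drug caused them.

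Recall is also uneven. At Visit 7, condition 1 looks back to dosing days 6 and 3 weeks earlier, while condition 2 reports on a capsule still taken daily.

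The assessment schedule is fixed by the protocol. An analysis plan cannot supply a pre-dose score that was never collected.

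**Working it through.** The protocol states no figure on this point, so there is nothing to reproduce. The schedule was read as set out above. The arithmetic below only illustrates possible size, and its symptom rates and correlations are assumptions.

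**Single symptom.** The items and scoring rule are not shown, so there are two alternative readings. They should not be combined.

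*Reading A: patients report what is still present at Visit 7.* Assume 50% of each arm have sleep difficulty at entry, it resolves in 60% of one arm and 40% of the other, and no new cases arise.
- Visit 7 rates: 0.50 × 0.40 = 20% versus 0.50 × 0.60 = 30%, a 10-point gap with no drug effect.
- Plain change from baseline: 20 − 50 = −30 versus 30 − 50 = −20, still a 10-point gap.
- New or worse than baseline: 0 versus 0.

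*Reading B: patients report anything present at any time in the 6 weeks.* With the same entry rate, 50% versus 50% are counted and the spurious gap disappears. A true difference is obscured instead. Assume 40% have the symptom at entry and all of them are counted, and that new symptoms arise in 15% versus 5% of the remainder.
- All reported: 0.40 + 0.60 × 0.15 = 49% versus 0.40 + 0.60 × 0.05 = 43%. The gap is 0.60 × 0.10 = 6 points. With 30 per arm (section 4.2.1), its standard error is √[(0.49 × 0.51 + 0.43 × 0.57)/30] = 12.8 points, so the gap is 0.47 standard errors.
- New symptoms only, over all patients: 9% versus 3%. The gap is again 6 points, but the standard error is √[(0.09 × 0.91 + 0.03 × 0.97)/30] = 6.1 points, so the gap is 0.99 standard errors.

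The loss under Reading B is background noise: the same gap carries about half the signal.

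**Total score.** Suppose a side-effect score has correlation r with week-6 depression and there is no true tolerability difference. The induced standardised difference is r × D/SD, where D is the difference between arms in week-6 QIDS. Inputs:
- SD = 5.6. This is the pilot SD of change in section 4.2.1, borrowed here for the week-6 score.
- D = 9.2/2 = 4.6. This is half the pilot reduction and was meant there for 1 mg psilocybin, not escitalopram, so it serves only as a large example. D = 2 and D = 0 are the alternatives.
- 30 per arm, two-sided t-test at 5%, 20,000 simulated trials per setting.

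| D | r | Induced difference (SD) | p < 0.05 |
|---|---|---|---|
| 4.6 | 0.2 | 0.16 | 9.6% |
| 4.6 | 0.3 | 0.25 | 15.1% |
| 4.6 | 0.5 | 0.41 | 34.3% |
| 2 | 0.2 | 0.07 | 6.1% |
| 2 | 0.3 | 0.11 | 6.8% |
| 2 | 0.5 | 0.18 | 10.5% |
| 0 | 0.2 to 0.5 | 0 | about 5% |

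**The case against.** A reader might infer that leftover depressive symptoms are certain to be scored as side-effects and that the tolerability comparison as a whole is confounded with efficacy. The documents do not support that.

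- The items, the rater and the attribution rule are not shown. The title of the cited reference concerns inter-rater reliability of a side-effects scale, which suggests rater judgement that could exclude some persisting symptoms. This stands, so the claim is limited to what can be counted. A rater without a pre-dose record would still depend on the patient's memory of onset.
- Randomisation balances entry symptoms on average. Without an efficacy difference there is no between-arm bias, and the prediction of a different side-effect profile is itself framed under comparable efficacy. This stands. But section 1.1 also hypothesises superiority, and the loss of signal under Reading B does not need an efficacy difference.
- That the questionnaire is given once rests on silence in lists that are not exhaustive. Section 2.7 says what measures will include. The Study Timeline shows main assessments and omits this questionnaire even at Visit 7. Section 2.1.2 mentions side-effect measures without naming an instrument or schedule, and section 4.2.3 has unspecified secondary measures at screening. This stands as a caution, and is itself a reason to state the schedule.
- Other data cover part of the gap. Adverse events are collected from consent with causality grading (sections 7.4 and 7.5). Sexual dysfunction, the one side-effect prediction named, has a before-and-after scale, as do akathisia and emotional side-effects. QIDS, HAM-D and MADRS give pre-dose information on depressive symptoms. End-of-session scales and the interviews at Visits 4 and 6 record the dosing days close to the time. All of this narrows the point to one instrument; none of it gives that instrument a baseline.

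**Conclusion.** The point holds for this questionnaire only. As written, its one stated administration is at Visit 7 with 6-week recall, so it cannot by itself separate new symptoms from those present at entry. The effect is a loss of signal for true differences and, conditional on unequal residual depression at week 6, a spurious tolerability difference in favour of the arm that improved more.

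The size is not derivable from the documents. Under the assumptions shown, the false-positive rate ranges from about 5% with equal efficacy, through 6% to 11% for a 2-point QIDS difference, to 10% to 34% for 4.6 points. The single-symptom figures depend on how the questionnaire is scored, which is not stated.

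This is an inexpensive improvement to a secondary comparison. It does not show that the tolerability aim fails, and adverse-event collection and the domain scales with before-and-after measurement are untouched.

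**What to change.** State the questionnaire's schedule. Give the same instrument before dosing at Visit 2, the day before dosing session 1, and optionally before dosing at Visit 5, which shortens recall to about 3 weeks. Compare arms on symptoms new or worse than the Visit 2 score. A plain change score is not enough, because improvement in depression passes straight into it, as Reading A shows.

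The cost is some extra minutes at one or two existing visits, in a battery already put at about 75 minutes. A Visit 2 baseline taken after washout may also include withdrawal symptoms, which would raise the baseline and could hide later effects. Patients who underwent washout should therefore be identified in the comparison. Worsening depression would still register as new or worse, so the result should be read beside the depression scores.
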